A recent systematic review and meta-analysis examined 28 studies looking at outcomes of TNT for locally advanced rectal cancer; these included a total of 2,688 patients treated with TNT. The pooled pCR rate was 22.4%. Ten of the studies compared pCR rates for treatment with TNT versus standard CRT; pooled analysis showed that TNT increased the odds of pCR by 39% (OR 1.40, 95% CI 1.08-1.81, p=0.01). Seven studies compared

survival outcomes; patients treated with TNT had significantly better OS (HR 0.73, 95% CI 0.59-0.9, p=0.004).

In metastatic colorectal cancer, a triplet regimen with 5FU, oxaliplatin and irinotecan (FOLFOXIRI) has been shown to be superior to standard doublet chemotherapy. This intensified regimen has been explored in combination with bevacizumab and CRT in rectal cancer in order to maximize response. This study enrolled 49 patients with T4 or high-risk T3 rectal cancer; they received 6 cycles of FOLFOXIRI plus bevacizumab followed by CRT and then surgery 8 weeks later. pCR with this regimen was 36%. Grade 3-5 toxicities during induction chemotherapy and CRT included thrombocytopenia (2%), neutropenia (42%), febrile neutropenia (4%), diarrhea (12%), stomatitis (4%), asthenia (6%), hypertension (2%), aminotransferases elevation (2%) and rectovaginal fistula (2%). One patient died due to bowel perforation (a known bevacizumab-related adverse event) and sepsis after the first cycle of chemotherapy and another patient discontinued induction treatment after acute kidney injury (followed by complete recovery). One patient had pneumonia after chemotherapy and went directly to surgery.

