### **2.2.3 Short course radiation (SCRT)**

While the pivotal German Rectal trial established preoperative CRT as standard of care for locally advanced rectal cancer in the United States, multiple trials have demonstrated the efficacy of SCRT. The advantages of SCRT over long-course CRT include excellent compliance, cost-effectiveness, and better integration with systemic therapy. While there were initial concerns for lack of downstaging of bulky tumors and inferior outcomes with low-lying tumors with SCRT, the addition of a delay (during which chemotherapy can be delivered) prior to TME has resulted in comparable outcomes with SCRT as CRT.

The Polish Colorectal Study group trial randomized patients with cT3 or cT4 rectal cancer (>60% of patients had T4 tumors; over half of patients had tumors <5 cm from anal verge) to either preoperative SCRT (5 x 5 Gy) followed by 3 cycles of FOLFOX-4 or CRT (50.4 Gy of RT in 28 fractions of 1.8 Gy each concomitantly with oxaliplatin, boluses of fluorouracil, and folinic acid). These regimens were chosen to ensure equivalent treatment time and interval from initiation of RT to TME. The proportion of patients with a pCR was greater among patients who received SCRT and consolidation chemotherapy than among patients who received CRT, but the difference did not reach statistical significance (16% versus 12%, p=0.17). There was no difference in DFS, OS or long-term complications.

Washington University School of Medicine (St. Louis, MO) reported good overall response to a preoperative regimen that comprised SCRT followed by 4 cycles of FOLFOX with TME performed 4 to 9 weeks after preoperative chemotherapy. At surgery, 70% of patients had ypT0-2 residual disease, including 25% with pCR^44. A matched pair analysis from the same group showed that compared to standard preoperative CRT, SCRT with TNT (modified FOLFOX x 6 cycles) had higher T-downstaging and superior distant metastasis-free survival and DFS. Grade 3-5 hematologic toxicities were higher with SCRT and TNT (22% versus 0%, p<0.001).

Grade 3-5 gastrointestinal toxicities were lower with SCRT and TNT compared to CRT, although not statistically significant (6% v 13%, p=0.24).

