### 6.1.1 Hematologic Toxicity

- For ANC 1,000/mm^3–1,200/mm^3: Delay chemotherapy until ANC > 1,200/mm^3 then resume chemotherapy at the same dose level.
  - Second or More Occurrence of ANC 1000/mm^3-1200/mm^3: Delay chemotherapy until ANC > 1,200/mm^3 then resume FOLFIRINOX with one dose level reduction for all subsequent cycles. **NOTE:** The dose of leucovorin is not reduced.
- For ANC < 1,000/mm^3: Delay chemotherapy until ANC > 1,200/mm^3, then resume chemotherapy with one dose level reduction for all subsequent cycles. **NOTE:** The dose of leucovorin is not reduced.
- For Febrile Neutropenia (defined as ANC < 1,000/mm^3 and temperature > 100.5°F): Delay chemotherapy until resolution of fever and ANC > 1,200, then resume chemotherapy with one dose level reduction for all subsequent cycles. **NOTE:** The dose of leucovorin is not reduced.
- For Platelets 50,000 K/ul – 75,000 K/ul: Delay chemotherapy until platelets > 75,000 then resume chemotherapy at the same dose level.
  - Second or More Occurrence of platelets 50,000 K/ul - 75,000 K/ul: Delay chemotherapy until platelets > 75,000K/ul, then resume chemotherapy with one dose level reduction for all subsequent cycles. **NOTE:** The dose of leucovorin is not reduced.
- For Platelets < 50,000 K/ul: Delay chemotherapy until recovery to Plts > 75,000 K/ul then resume chemotherapy with one dose level reduction for all subsequent cycles. **NOTE:** The dose of leucovorin is not reduced.

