### **12.2 Interim analyses**

We plan to conduct one interim analysis for futility. We will assess efficacy and toxicity during this analysis. Following an optimal Simon 2 stage design for efficacy, we will enroll 17 patients and assess cCR. If less than or equal to 3 patients have cCR we will stop the study for futility. Otherwise, we will continue the study and enroll 20 more patients. At the end of the study, if 11 or more patients have cCR, we will deem this treatment strategy acceptable.

We assume an acceptable toxicity rate of  $\leq 25\%$  with an unacceptable toxicity rate of 40%. Thus, at the interim analysis, if 7 or more patients have toxicity (defined as non-hematologic CTCAE v5 grade 4 or higher toxicity at least possibly related to treatment), we will stop the study and consider the treatment strategy unsafe. Otherwise, we will continue the study and conclude that the treatment is acceptable if 13 or fewer patients of the 37 total patients have toxicities. Assuming that the true toxicity rate is 25%, the probability of stopping the study at the interim analysis for toxicity is 11% and for rejecting the null hypothesis is 13%. If the true toxicity rate is 40%, the probability of stopping the study early is 55% and probability of rejecting the null hypothesis is 74%.

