### **12.7 Criteria for future studies**

Based on our criteria stated above, if the study is not stopped at the interim analysis, if 11 or more patients of the 37 patients have cCR and 13 or fewer patients have grade 4+ non-hematologic toxicity, we will deem this treatment strategy acceptable.

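### The only numeric safety rule judges non-hematologic grade 4+ events against 25% and 40% limits that the plan never justifies for that event, and its wording can leave a febrile neutropenia death uncounted

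*Combined protocol and SAP*

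**What the plan says.** Section 12.2 of the combined protocol and SAP sets one interim look, at 17 patients, for efficacy and toxicity. The toxicity arm stops the trial "if 7 or more patients have toxicity (defined as non-hematologic CTCAE v5 grade 4 or higher toxicity at least possibly related to treatment"). The design rates are 25% or less (acceptable) and 40% (unacceptable). If the trial continues, the treatment is acceptable on safety with 13 or fewer events among 37 patients. Section 12.2 prints these probabilities:

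- at a true rate of 25%, early stop 11% and rejection 13%;
- at a true rate of 40%, early stop 55% and rejection 74%.

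Section 12.7 repeats the definition as half of the final decision, alongside the response criterion: "13 or fewer patients have grade 4+ non-hematologic toxicity, we will deem this treatment strategy acceptable".

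Neither section cites a source for 25% or 40%, and no section gives an expected rate of non-hematologic grade 4+ toxicity. The graded rates in Sections 2.1 to 2.2.3 are grade 3-4 or grade 3-5; one example reads "Grade 3-5 gastrointestinal toxicities were lower with SCRT and TNT compared to CRT" (6% v 13%).

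The chemotherapy dose-modification guidance places febrile neutropenia in Section 6.1.1, Hematologic Toxicity: "For Febrile Neutropenia (defined as ANC" below a threshold, with fever.

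**The concern.** A safety limit can be judged only against the rate expected for the event it counts. Here the event is narrow (grade 4 or 5, non-hematologic, at least possibly related), while the limits are wide and have no stated basis for it. If the expected rate lies well below 25%, the boundary can tolerate a large excess over expectation, and passing it carries little information. Grades 4 and 5 are also pooled, so nothing in the rule treats deaths separately.

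The second issue is the organ-class filter. Neutropenia is foreseeable with triplet chemotherapy: Section 2.2.2 reports 42% grade 3-5 neutropenia and 4% febrile neutropenia for a FOLFOXIRI-based regimen. If an assessor follows the protocol's own heading and files febrile neutropenia as hematologic, a treatment-related death could fall outside the trial's only numeric safety rule and outside half of the Section 12.7 verdict.

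**Working it through.** **Inputs.** From Section 12.2: 17 patients at stage 1, 20 more at stage 2, stop at 7 or more of 17, unsafe at 14 or more of 37 (13 or fewer is acceptable). The toxicity rule is taken alone, without the futility stop.

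**Formulas.** For a true rate p:

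- Early stop: E(p) = P(Bin(17, p) ≥ 7).
- Ever called unsafe: U(p) = E(p) + Σ over x = 0 to 6 of P(Bin(17, p) = x) × P(Bin(20, p) ≥ 14 − x).

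**The plan's own figures.**

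- p = 0.25: E = 0.1071; stage 2 adds 0.0247; U = 0.1318. Printed: 11% and 13%.
- p = 0.40: E = 0.5522; stage 2 adds 0.1876; U = 0.7398. Printed: 55% and 74%.

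All four reproduce.

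**The same rule at other true rates.** The documents give no grade 4+ rate, so the rows below 25% are assumptions shown as a range.

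| True rate | Early stop | Ever called unsafe |
|---|---|---|
| 5% | 0.001% | 0.001% |
| 10% | 0.08% | 0.08% |
| 15% | 0.83% | 0.86% |
| 20% | 3.8% | 4.2% |
| 25% | 10.7% | 13.2% |
| 28% | 17.2% | 22.4% |
| 40% | 55.2% | 74.0% |

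The early-stop chance reaches 1% at a true rate of about 15.5%, 5% at about 21% and 50% at about 38.5%.

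**What passes.** 6/17 = 35% continues; 13/37 = 35% is acceptable.

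**Background rates.** For FOLFOXIRI plus bevacizumab with chemoradiotherapy (Section 2.2.2), the listed non-hematologic grade 3-5 items are diarrhea 12, stomatitis 4, asthenia 6, hypertension 2, aminotransferases 2 and fistula 2. The sum is 12 + 4 + 6 + 2 + 2 + 2 = 28% if no patient had two of them, and 12% if they overlap fully. E(0.12) = 0.23% and E(0.28) = 17.2%. Adding the death described separately (1 of 49, 2%) gives at most 30%, with E(0.30) = 22.5%. Grade 4+ events are a subset of grade 3-5 events, so their rate in that study cannot be higher than the grade 3-5 rate. How much lower it is, the documents do not say.

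Other background figures differ widely: 6% gastrointestinal (Section 2.2.3), 27% versus 40% acute grade 3 or 4 (Section 2.1), up to 10 + 9 + 7 + 3 + 3 + 1 = 33% for CAPOX items and 42% for skin toxicity during chemoradiotherapy (Section 2.2.2).

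**Febrile neutropenia.** Section 12.2 admits only non-hematologic events. Section 6.1.1 lists febrile neutropenia under the hematologic heading. Neither section says how a death with febrile neutropenia is classified. Coded as febrile neutropenia it can be left out; coded as sepsis or infection it could count.

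**The case against.** Three stronger readings are tempting, and the documents support none of them.

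- **That the limits were taken from grade 3+ data.** Section 12.2 cites nothing. The background rates run from 6% to 42% across different regimens and single out no threshold. Sections 12.2 and 12.7 also agree on grade 4+, so this is not a slip in one sentence.
- **That the rule almost never fires or cannot detect harm.** That depends on an assumed rate. At 40%, the rate the plan calls unacceptable, the rule stops early 55% of the time and rejects 74% of the time. Having declared up to 25% acceptable, the plan intends not to stop at 10% or 15%. Counting grade 3+ would not by itself cure this: at true rates of 12% to 20% the 7-of-17 boundary still stops only 0.23% to 3.8% of the time.
- **That fatal febrile neutropenia is expressly excluded.** Section 6.1.1 is dose-modification guidance, introduced in Section 6.1 as recommendations, and does not define endpoint events.

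The rule is also not the only safeguard. Serious events of grade 3 and above are reported promptly (Section 7.2.1.1), unanticipated problems within 24 hours (Section 7.2.2.1), and the monitoring committee regularly reviews serious events (Section 11.2). This is real protection for patients, but it carries no numeric boundary and does not make the Section 12.7 verdict more informative. How much toxicity to tolerate is a judgement for the sponsor. What remains is that the judgement is unexplained for the event counted and that the classification of deaths is left open.

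**Conclusion.** The point holds in two parts. First, the 25% and 40% limits have no stated basis for non-hematologic grade 4+ events, and performance is shown only at those two rates. The printed arithmetic is right. If the true rate were 10% to 20% (assumed), the interim rule would stop 0.08% to 3.8% of the time, and the toxicity rule alone would return acceptable in about 99.9% to 95.8% of trials (100% minus the 0.08% to 4.2% ever called unsafe). A pass would then say little. Second, the non-hematologic filter, read with Section 6.1.1, can leave a febrile neutropenia death uncounted. This is an ambiguity rather than a stated exclusion, but it concerns the most serious outcome the rule is meant to capture.

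**What to change.** In Sections 12.2 and 12.7:

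1. Count every grade 5 event at least possibly related to treatment, whatever its organ class.
2. State the expected rate of the exact event counted, with its source.
3. Reconcile the 25% and 40% limits with that event and give the reason for them. No particular limit or grade is proposed here.
4. Restate the operating characteristics of the boundaries at 17 and 37 patients, including at the expected rate.

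The sample size does not change, and adverse events are already graded and recorded (Section 7.2.3), so the work is amendment wording and a recalculation. The downside is a slightly higher chance of a safety stop. As an illustration, if counting all treatment-related deaths raised the counted rate from 10% to 12% (assumed), the early-stop chance would go from 0.08% to 0.23%. Any change to the limits would have its own effect, to be computed once they are chosen.

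The documents do not say whether the 17-patient look has taken place. If it has, the amendment should record that the change was made after that look.

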### **11.2 Data and Safety Monitoring Plan**

The Stanford Cancer Institute Data and Safety Monitoring Committee (DSMC) will be the monitoring entity for this study. The DSMC will audit study-related activities to determine whether the study has been conducted in accordance with the protocol, local standard operating procedures, FDA regulations, and Good Clinical Practice (GCP). This may include review of the following types of documents participating in the study: regulatory binders, case report forms, eligibility checklists, and source documents. In addition, the DSMC will regularly review serious adverse events and protocol deviations associated with the research to ensure the protection of human subjects. Results of the DSMC audit will be communicated to the IRB and the appropriate regulatory authorities at the time of continuing review, or in an expedited fashion, as needed.

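### The only numerical safety rule counts a treatment-related death the same as a grade 4 event and sets no separate limit for deaths, so it is nearly insensitive to mortality

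*Combined protocol and SAP*

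**What the plan says.** Section 12.2 has one interim look, after 17 patients. The toxicity that counts is "defined as non-hematologic CTCAE v5 grade 4 or higher toxicity at least possibly related to treatment". The study stops for toxicity "at the interim analysis, if 7 or more patients have toxicity". Otherwise it goes on, and the investigators will "conclude that the treatment is acceptable if 13 or fewer patients of the 37 total patients have toxicities". The section gives 25% as the acceptable rate and 40% as the unacceptable rate, with stopping and rejection probabilities of 11% and 13% at 25%, and 55% and 74% at 40%.

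Section 12.7 joins the final toxicity limit to the efficacy limit of 11 or more clinical complete responses (cCRs): if that is met and "13 or fewer patients have grade 4+ non-hematologic toxicity, we will deem this treatment strategy acceptable".

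Outside section 12, section 7.2 covers the reporting of serious adverse events (SAEs), fatal ones included, and of unanticipated problems. Section 11.2 says "the DSMC will regularly review serious adverse events and protocol deviations associated with the research". Neither section names a number of deaths that leads to a pause or a stop, and 12.7 does not mention the DSMC.

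**The concern.** Grade 4 or higher includes grade 5, and the count is per patient. A patient who dies of treatment therefore moves the rule by one step, the same as a patient whose grade 4 event resolves. A limit set to tolerate grade 4 events in about a third of patients (6/17 = 35.3%, 13/37 = 35.1%) gives little protection against a death rate that is far lower but still unacceptable.

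Patients have non-metastatic disease, and section 4.5 names standard treatment including total mesorectal excision as the alternative, so excess related mortality is the safety signal that matters most. The rule is also checked only once before the end. At the 0 to 1 patients per month expected in 12.6.1, the first 17 take at least about 17 months to enroll, and after that look no toxicity boundary applies until the end of the study.

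There is a second gap. The definition covers non-hematologic toxicity only and does not say how a death with a hematologic cause is counted. Such a death might not enter the count at all.

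**Working it through.** **Inputs.** From 12.2: stop at ≥7 of 17; not acceptable at ≥14 of 37 (the complement of 13 or fewer); 20 patients in stage 2. The related-death rates below are assumptions, shown over a range.

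**Formula.** With X₁ ~ Bin(17, p) and X₂ ~ Bin(20, p):

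- early stop = P(X₁ ≥ 7)
- rule fires = P(X₁ ≥ 7) + Σ over x = 0..6 of P(X₁ = x) · P(X₂ ≥ 14 − x)

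**Step 1: the plan's own figures.**

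| True rate of counted events | Early stop | Fires overall | Printed |
|---|---|---|---|
| 25% | 0.107 | 0.107 + 0.025 = 0.132 | 11%, 13% |
| 40% | 0.552 | 0.552 + 0.188 = 0.740 | 55%, 74% |

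All four agree, so the boundaries are read correctly and the plan's arithmetic is sound. The issue is what the rule counts.

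**Step 2: the same rule when related deaths are the only qualifying events.**

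| Assumed related-death rate | Expected deaths in 37 | Rule fires |
|---|---|---|
| 2% | 37 × 0.02 = 0.74 | 0.00000002 |
| 5% | 1.85 | 0.00001 |
| 10% | 3.7 | 0.0008 |
| 15% | 5.55 | 0.009 |
| 20% | 7.4 | 0.042 |

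The 15% row also applies when deaths and grade 4 events together reach 15% of patients, because the rule does not distinguish them.

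**Step 3: the literal extremes.** Six related deaths in 17, or 13 in 37 with no more than 6 in the first 17, would not cross the toxicity boundary. At a 10% death rate, 6 or more in 17 has probability 0.005 and 13 or more in 37 has probability 0.00003.

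**Step 4: what a separate death trigger would do.** Taking the second related death as an example, the probability of reaching it within n patients is 1 − (1 − p)ⁿ − n·p·(1 − p)ⁿ⁻¹.

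| Assumed related-death rate | n = 17 | n = 37 |
|---|---|---|
| 2% | 1 − 0.709 − 0.246 = 0.045 | 1 − 0.474 − 0.358 = 0.17 |
| 5% | 1 − 0.418 − 0.374 = 0.21 | 1 − 0.150 − 0.292 = 0.56 |
| 10% | 1 − 0.167 − 0.315 = 0.52 | 1 − 0.020 − 0.083 = 0.90 |

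The n = 37 column assumes that all 37 patients are enrolled.

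**Scale.** Section 2.2.2 describes a 49-patient study of FOLFOXIRI plus bevacizumab followed by chemoradiotherapy, in which "One patient died due to bowel perforation" and sepsis. That is 1/49 = 2.0% (exact 95% CI 0.05% to 10.9%). The protocol itself calls the perforation a known bevacizumab-related event, and this trial's regimens contain no bevacizumab. The figure gives scale only; it is not an estimate for this regimen.

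**The case against.** A reader might infer from Step 3 that the plan would let a trial with 6 related deaths run on, or would call 13 related deaths in 37 acceptable. The documents do not support that, for three reasons.

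- The extremes require every counted event to be a death. They are improbable even at 10% mortality, and no section suggests mortality of that order. Section 7 describes the chemotherapy and radiation as standard care.
- The verdict in 12.7 also needs at least 11 cCRs, and the study must first pass the interim look with at least 4 in 17. If all 13 deaths came before response assessment, 6 of them in stage 1, the other 24 patients would have to supply 11 cCRs (11/24 = 46%). Both efficacy limits would then be met with probability 0.33 if those patients' true cCR rate were 40%, and 0.0035 if it were 20%. Deaths after assessment are not restricted in this way.
- Deaths are also handled case by case. SAEs of grade 3 and above are reported promptly, unanticipated problems within 24 hours, and the DSMC reviews SAEs regularly. Slow accrual leaves time for review between events. Not crossing the boundary does not mean that the study must continue.

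Two further objections have force. The low probabilities in Step 2 come largely from how high the limits are: a pooled limit of 3 in 17, for illustration, would be reached with probability 0.24 at a 10% death rate. It would therefore be wrong to say that no pooled limit could detect deaths. Nor does anything in the documents single out the second death as the right trigger, and a trigger checked at each event at 2 is not matched for false alarms with a single-look limit at 7.

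These points limit the claim but do not remove it. The limits in the plan are the high ones, a small cluster of related deaths leaves them uncrossed unless many grade 4 events occur as well, and the bodies that could act have no stated death criterion.

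**Conclusion.** The point holds as a gap in the pre-specified rule. It is neither an arithmetic error nor a claim that deaths would go unreviewed. The only quantitative safety boundary gives a related death the weight of a grade 4 event, and it would fire with probability about 0.00001 at 5% related mortality and 0.0008 at 10%. These figures assume that deaths are the only qualifying events; accompanying grade 4 events raise the probability, to 0.009 when the total is 15%. The death rates are assumed, because the documents give none for this regimen. DSMC and IRB review softens the gap but supplies no trigger and does not enter the 12.7 verdict. The change is inexpensive and should be made.

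**What to change.** - **Section 12.2:** add a grade 5 rule, checked at each event, for any death at least possibly related to study treatment, whether its cause is hematologic or non-hematologic. When a number of such deaths set by the sponsor is reached, accrual pauses for documented DSMC review. Print the rule's operating characteristics beside the existing 11, 13, 55 and 74% figures. The second-death trigger in Step 4 is an example of the calculation, and the choice of number remains with the sponsor and the DSMC.
- **Section 12.7:** state that the strategy is not deemed acceptable if this boundary was crossed and the DSMC did not clear the study to continue.
- **Section 12.5.2:** report related deaths on their own line.

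The cost is protocol wording and one more monitoring item, with no extra patients or procedures. The downside is an occasional unnecessary pause: with the example trigger and 2% related mortality, the chance is 4.5% by 17 patients and 17% by 37. The consequence would be a review, not termination.
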